2 RATIONALE

This human comedogenicity test panel(s) is being conducted on product(s) making the claim of “non-comedogenic”.

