4 OVERALL STUDY DESIGN AND PLAN DESCRIPTION

A single center, evaluator blinded, randomized, four-week clinical test panel(s). This human comedogenicity test panel(s) is being conducted in order to assess the comedogenic potential of the test material(s) and determine if the test material(s) induce microcomedones under repetitive patch test conditions. The target population for each test panel is adult men and women (age 18 through 45 years), who are acne-prone and have large pores on the back and/or a history of acne vulgaris on the face or back. Subjects will be patched on the upper back with test material dosed patches and an undosed occlusive patch (negative control) every Monday, Wednesday, and Friday for 4 consecutive weeks. Each test site will be graded for irritation after each patch removal. After 12 full patching sessions, a follicular biopsy will be collected from the test material and control sites, and graded for microcomedones.

Protocol Activity:	Visit 1 Screening/Baseline	Visit 2- Visit 12 (Conducted Monday Wednesday, and Friday for 4 consecutive weeks) **	Make-up visit* (if needed)	Visit 13
Informed consent with HIPAA disclosure	X			
Collect demographics, general medical history & concomitant medications	X			
Review of potential test sites (upper back) by PI (or designee)	X			
Eligibility review and subject qualification by PI (or medically qualified designee)	X			
Interview for compliance		X	X	X
Remove TM, control, and negative control dosed patches from test sites		X	X	X
Clinical NACDG grading of test sites by PI or designee		X	X	X
Test sites marked (to be remarked as needed)	X	X	X	
Test sites wiped with distilled or deionized water and air dried	X			
Randomization of TM, control, and negative control on test sites	X			
Apply TM, control, and negative control dosed patches on test sites	X	X	X	
Dispense study visit calendar to subject	X			
Review study instructions with subject	X			
Collect follicular biopsy from each test site				X
Collect/record AEs and changes in health/medications	X	X	X	X
Subject disposition				X

* Denoted activity will only occur if subject missed one of the scheduled visits from visits 2 to 12 and requires a make-up visit

** See Study Duration in section 5

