8 INVESTIGATIONAL STUDY MATERIALS

8.1 IDENTITY OF INVESTIGATIONAL STUDY MATERIALS

The test material(s) will be manufactured and packaged by the Sponsor. The ingredient list and Safety Attestation letter for each product will be provided to the PI for review and submission to the IRB. The ingredient list and Safety Attestation letters will be filed in the Site Master File for the test panels.

Formula numbers of the test material(s) will be provided via the protocol addendum form prior to the conduct of each study.

A label will be affixed to each test material. The label may contain (but is not limited to) fields for the following information:

- Reference Number
- Type of test material
- Directions
- Net Contents or Net Weight
- Formula number
- Storage Information
- **“For Investigational Use Only”**

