9 INVESTIGATIONAL PLAN

9.1 STUDY PROCEDURES AND EVALUATION SCHEDULE

Pre-Study:

Candidate subjects will be recruited using IRB-approved materials. Interested candidates will be scheduled for Visit 1.

Screening/Baseline: Visit 1

Interested candidates will report to the site and take part in the following procedures:

1. Prospective candidates will be sequentially assigned a 2-digit screening number preceded by "S" (e.g. S01).
2. Subjects will be given an IRB-approved ICD and IRB-approved Supplemental Consent form (when applicable) to read and sign. They will have all of their study related questions answered by the Investigator or designated staff, and if they agree, they will sign 2 copies of the ICD and Supplemental Consent form (when applicable). They will retain 1 copy, and 1 will be kept in the study file.
3. Subjects will complete a health and eligibility questionnaire and a medical and medication history questionnaire.
4. Potential test sites (upper back) will be examined by the Investigator or designee for qualification criteria.
5. The screened subjects that meet all eligibility requirements will be enrolled into the study and assigned a subject number as describe in the "Randomization" section.
6. A delegated clinician will delineate up to six test sites on the subject's upper back, to the right and left of the spine, using an indelible marker. Each test site will be a 4 cm² and no closed than 2 cm² from each other. The test sites may be re-delineated at subsequent visits as needed
7. The test sites will be wiped with distilled or deionized water and allowed to air dry prior to patching.
8. The test material dosed patches and an undosed negative control patch will be applied to each subject's upper back according to the predetermined randomization.
9. Subjects will be provided with a calendar of study visits and study instructions. Subjects will be reminded of sun exposure/tanning and swimming/hot tub restrictions. Subjects will also be instructed to reinforce the edges of the patch with a bandage tape in the event that the tape applied in the clinic does not adhere.

Interim Visits: Visit 2 – Visit 12

Visit 2 will be completed 48-72 hours post Visit 1. Visits 3-12 will occur 48-72 hours post each subsequent visit, i.e., Monday, Wednesday, and Friday for four consecutive weeks. Subjects will report to the site at their scheduled visit time and will participate in the following procedures at each interim visit:

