9.2 STUDY INSTRUMENT(S)

Follicular Biopsies:

Follicular biopsies will be collected from each patch site at Visit 13 or make-up visit for each subject. The following procedures will be followed for follicular biopsy collection:

- The test sites will be gently cleansed with warm soapy, water and patted dry.
- A glass slide containing a drop of cyanoacrylate glue will be held against each site until it has dried.
- The slide will then be removed slowly, so as to extract follicles and their contents.
- The specimen slides will be stored in labeled slide boxes until graded.
- The specimens collected using the cyanoacrylate follicular biopsy technique will be evaluated by a trained grader using a stereomicroscope (magnification ratio of 0.8). Hyperkeratotic follicles (microcomedones) will appear as cylindrical horny impactions surrounding extracted vellus hairs.

Specimens will be graded using a 5-point global assessment scale as follows:

- 0 None (0%, No microcomedones)
- 0.5 Slight (1-24% Smallish horny masses)
- 1 Mild (25-49% Smallish horny masses)
- 2 Moderate (50-74% Moderately sized horny masses)
- 3 Severe (75-100% Larger globoid microcomedones)

The results from the microcomedone grading of the follicular biopsies will be recorded using the Stephens Electronic Data Capture (EDC) system, if available, which documents the identity of the evaluator/technician as well as the time and date of all entries, or all corrected entries. Subject data can also be provided by Stephens at the Sponsor's request. Paper grading forms will be completed if EDC is unavailable. Any test site with a NACDG grading score of 2 or greater may not receive a follicular biopsy, which will be noted in the appropriate source documents.

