Demographic data and baseline characteristics will be summarized for all subjects who are enrolled in the study. For continuous variables, descriptive statistics including number of subjects (N), mean, median, standard deviation (SD), minimum (MIN) and maximum (MAX) values will be presented. For categorical variables, the frequency and percentage of each category will be provided.

A descriptive statistical summary will be provided for the global assessments of microcomedone data from biopsies for the test material and control sites. The descriptive statistical summary includes the number of observations (N), mean, median, standard deviation (SD), minimum (MIN), and maximum

(MAX).

In addition, microcomedone scores will be analyzed using a mixed-effects model, where the test Material/negative control is a fixed effect and the subject is a random effect. Each test product will be compared to the negative control within the model frame. A test material will be considered positive for comedogenicity if it has a mean microcomedone value of 1.0 or greater, and is statistically greater than the mean microcomedone value for the negative control site.

All statistical tests will be 2-sided at significance level $\alpha=0.05$. P-values will be reported to 3 decimal places (0.000). No multiple testing corrections will be considered in the study. Statistical analyses are performed using SAS software version 9.30 or later series (SAS Statistical Institute). The results will be sent to the Sponsor along the raw data in a Microsoft Excel document at the completion of the study.

A test material is considered negative for comedogenicity as long as it satisfies 1 of the following 2 conditions: the microcomedone mean score is less than 1.0 and/or the mean score is not greater than the control with p-value < 0.05 .

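### Does fitting one residual variance to the whole panel make a product's comparison with control unreliable enough to change the Section 10 model?

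*Combined protocol and SAP*

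**What the plan says.** Section 10 specifies a mixed-effects model "where the test Material/negative control is a fixed effect and the subject is a random effect". It adds: "Each test product will be compared to the negative control within the model frame". It names neither a residual covariance structure nor a degrees-of-freedom method. A material is positive only if its mean score is at least 1.0 and it is significantly above the negative control (two-sided 0.05). Failing either condition makes it negative.

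The panel size is open. Section 9.1 says "A delegated clinician will delineate up to six test sites on the" upper back of each subject. Section 8.1 says "Formula numbers of the test material(s) will be provided via the protocol addendum form prior to the conduct of each study". Section 7 aims for 15 completers per panel. Section 9.2 says "Specimens will be graded using a 5-point global assessment scale as follows", with the values 0, 0.5, 1, 2 and 3. The Section 4 schedule has a row reading "Apply TM, control, and negative control dosed patches on test sites", which mentions a control beside the negative control.

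**The concern.** A random subject intercept with one residual variance treats every site as equally variable. The score has a floor at 0, so a bland material will usually vary less than a comedogenic one. With three or more sites, the standard error of each product-control difference then comes from the average spread of the whole panel. It is too small when the other products (the panel-mates) vary little and too large when they vary a lot.

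The p-value is half of the decision rule. Section 2 says "This human comedogenicity test panel(s) is being conducted on product(s) making the claim of" being non-comedogenic, so bland panel-mates, and hence p-values that are too small, seem the likelier direction. A product's label should not depend on which unrelated products share its panel. If the schedule's extra control were a real site, even a one-product panel would have three sites.

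**Working it through.** The plan gives no power, SD or expected control score, so there is no figure of its own to reproduce. From the documents: n = 15, k up to 6 sites, the five-level score and the two-part rule. Assumed: SDs, means, and a within-subject latent correlation of 0 to 0.5.

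**1. The mechanism is real.** With complete data the random-intercept model gives SE = sqrt(2 × MSE / 15) on 14 × (k − 1) df, with MSE pooled over all k sites. For k = 2 this is the paired t-test. For k = 6 there are 70 df and the critical t is 1.994. Take fixed data with control mean 0.5 and product mean 1.0:

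- The pair alone gives p = 0.0017.
- Four quiet mates (SD 0.26) give residual SD 0.33, SE = 0.33 × 0.365 = 0.12, p = 0.0001.
- Four widely spread mates (SD 1.1) give residual SD 0.95, SE = 0.95 × 0.365 = 0.35, t = 0.5 / 0.35 = 1.4, p = 0.153. The call flips.

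**2. When the call is exposed.** A product with mean below 1.0 is negative whatever its p-value. At a product mean of 1.0 and six sites, significance survives while the residual SD is below (1.0 − control mean) / (1.994 × sqrt(2/15)) = (1.0 − control mean) / 0.728. That is 1.37 for control 0, 1.10 for 0.2, 0.96 for 0.3 and 0.69 for 0.5. A large gap also settles the call: control 0.5 and product 2.0 stays positive (p = 0.003) beside mates split between 0 and 3. Exposure is therefore confined to products with mean at least 1.0 and a modest gap from control.

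**3. What the false-positive inflation needs.** Let product and control be identical at mean 1.0, with one latent spread for all materials, so that each score SD follows from its mean. For six sites and zero correlation, the average variance is V = (2 × 0.80² + 4 × s²) / 6, where s is the mates' SD. The SE is understated by the factor r = sqrt(0.64 / V), and the effective critical value is 1.994 / r. The approximate column is the normal tail; the simulated column covers correlations 0 to 0.5.

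| Mates' mean | s | V | r | 1.994 / r | Approx. type I error | Simulated |
|---|---|---|---|---|---|---|
| 0.2 | 0.40 | 0.320 | 1.41 | 1.41 | 16% | 12.5-17% |
| 0.6 | 0.67 | 0.513 | 1.12 | 1.78 | 7% | 7-8% |
| 1.0 | 0.80 | 0.640 | 1.00 | 1.99 | 5% | 5% |
| 1.5 | 0.86 | 0.706 | 0.95 | 2.09 | 4% | 4% |

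The inflated rows need an undosed control at the plan's own comedogenic threshold, with dosed sites on the same backs well below it. With mates at 1.0, at 1.5 or a mix of the two, simulated type I error is 3.9-5.4%, and false positive calls are 1.9-2.7% against 2.1-2.6% paired.

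**4. What paired tests would cost.** Error df fall from 70 to 14, and the critical t rises from 1.99 to 2.14. In the settings below the product truly has a mean above 1.0 and exceeds control, so a positive call is correct. Mates equal control.

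| Control | Product | Positive calls, pooled | Positive calls, paired |
|---|---|---|---|
| 0.5 | 1.05 | 50-57% | 41-52% |
| 1.0 | 1.5 | 40-61% | 33-54% |

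With control 0.2, product 1.05 and mates at 0.2, the two are level (61-62% and 60-62%).

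**5. The other alternative.** A separate residual variance per material with Satterthwaite df has type I error of 1.9-5.2% beside near-floor mates (mean 0.2, SD 0.28). It is conservative in places and still depends on mates through the common subject variance. It also needs a fallback when a site has no variation: if 90% of scores at a site are 0, all 15 are 0 with probability 0.9^15 = 0.21.

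**The case for a change.** The strongest case for a change is that a low control cannot be presumed. Subjects are chosen for a tendency to form comedones, and the control is an occlusive patch. If SDs are set directly, with control and product at 1.0 (SD 0.8) and mates at 0.6 (SD 0.55), type I error is 10-12% and false positive calls are 5-6%, against 2.2-2.4% paired. In the other direction, four mates at SD 1.04 cut correct positive calls to 30-48%, against 51-60% paired (product 1.05, control 0.5). A remedy would take a sentence or two and no new data.

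The arithmetic stands, and so does the point that the structure is unstated. The settings do not carry the conclusion. If acne-prone, occluded skin raises the control, it should raise the dosed sites on the same back too. If the products are bland, the undosed patch should be bland as well, and a low control usually settles the call. Four highly variable mates are unlikely in panels of products claimed to be non-comedogenic. With one such mate and three like control, positive calls are 53-60%, no worse than paired.

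The remedy also has a direction. Non-significance yields a negative verdict, so a less powerful test makes it easier for a comedogenic product to pass. Paired tests further lose a subject from a contrast when either biopsy is missing, and Section 9.2 allows that: "Any test site with a NACDG grading score of 2 or greater may not receive a follicular biopsy".

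**Conclusion.** No change is needed. Pooling the residual variance makes a contrast depend somewhat on its panel-mates, and in return gives more error df and better detection at 15 subjects. A contrast-specific variance reverses that exchange, at a cost of roughly 5 to 9 points of correct positive calls in the settings of step 4. Statisticians could reasonably choose either. The inflation of false positives requires dosed sites clearly below an undosed control near 1.0; with mates at or above control there is none.

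The missing residual structure is a gap that an analyst fills with the conventional default, and a paired result can be shown beside it without altering the plan. The schedule's separate control reads as a wording slip: the text of Section 4, Section 8.2, Section 9.1 and Section 10 all describe test material(s) and a single control.

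This rests on assumed SDs, correlations, control means and panel sizes, since the documents give none beyond the six-site limit. Data showing a control near 1.0 with much lower dosed sites would reopen the question. A panel with one product and one control is unaffected.

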11 MANAGEMENT OF INTERCURRENT EVENTS

11.1 AMENDMENTS TO THE PROTOCOL

Neither the PI nor Sponsor will modify this protocol without obtaining the concurrence of the other. The party initiating a modification will confirm it in writing. Amendments must be approved by the Sponsor and IRB prior to implementation.

Note that submission of administrative change/non-substantial amendments to regulatory authorities and/or IRB/IECs for approval prior to study implementation is determined after consultation with the local regulatory representative and/or IRB/IEC policy and may vary by country/region.

The only circumstance in which an amendment may be initiated prior to IRB approval is where the change is necessary to eliminate apparent immediate hazards to the subjects. In that event, the PI must notify the IRB and the Sponsor in writing within 3 working days after the implementation.

11.2 PROTOCOL DEVIATIONS

Protocol deviations should be avoided whenever possible. When a protocol deviation occurs, it must be captured on a Deviation Log.

The PI or designee will also contact the Study Manager, Contact with the Study Manager will be made as soon as possible in order to discuss the situation and agree on an appropriate action. If it is determined that the subject safety/well-being was affected, the IRB/IEC, if any, will also be notified. The final report will describe the deviation from the protocol and the circumstances requiring it.

11.3 ADVERSE EVENT REPORTING

11.3.1 Introduction

Timely, accurate, and complete reporting and analysis of safety information from clinical studies are crucial for the protection of subjects, investigators, and the Sponsor, and are mandated by regulatory

agencies worldwide. The Sponsor has established procedures in conformity with regulatory requirements to ensure appropriate reporting of safety information.

11.3.2 Definitions

11.3.2.1 Adverse Event (AE)

An AE is any untoward medical occurrence in a clinical study subject temporally associated with the clinical investigation, whether or not the event has a causal relationship to the subject's participation in the trial. It is therefore any unfavorable and unintended sign (including an abnormal finding), symptom, or disease that occurs during the trial. This can include any occurrence that is new in onset, an aggravation of severity/frequency of a baseline condition, or abnormal results of diagnostic procedures, including laboratory test abnormalities.

Examples of AEs include but are not limited to:

- Abnormal test findings,
- Clinically important symptoms and signs,
- Changes in physical examination findings,
- Hypersensitivity, and
- Progression/worsening of underlying disease.

Any change in existing medical condition (Medical History) would be considered an AE and recorded appropriately.

Additionally, they may include the signs or symptoms resulting from:

- Investigational product overdose,
- Investigational product withdrawal,
- Investigational product abuse,
- Investigational product misuse,
- Investigational product interactions,
- Medication errors,
- Investigational product dependency,
- Exposure *in utero*, and
- Study related procedure.

The criteria for determining whether an abnormal objective test finding should be reported as an AE are as follows:

- Test result is associated with accompanying symptoms, and/or
- Test result requires additional diagnostic testing or medical/surgical intervention, and/or
- Test result leads to a discontinuation from the study, significant additional concomitant treatment, or other therapy, and/or
- Test result is considered to be an adverse event by the PI or the Sponsor.

Merely repeating an abnormal test, in the absence of any of the above conditions, does not constitute an AE. Any abnormal test result that is determined to be an error does not require reporting as an AE.

Expected AE

All investigational products have the potential to cause some uncomfortable effects or other reactions. Signs and symptoms of erythema, edema, scaling/dryness, itching, burning, stinging, and tingling are

considered clinical endpoints if they are mild in nature and should not be reported as AE. These conditions may or may not resolve over time. Symptoms that are persistent and moderate to severe in nature, or that involve elevation (e.g. edema, papules, vesicles, spreading) will be considered adverse events (AEs). The Investigator or designee will have the final authorization to determine if a reaction will be considered an AE.

If a subject is discontinued due to worsening of a sign or symptom (including worsening of the signs and or symptoms recorded as part of the evaluations), then it should be recorded as an AE.

Treatment Emergent AE (TEAE)

TEAE is defined as any event not present prior to the initiation of the IPs. Note that AEs will be summarized for all subjects who signed the ICD, differentiating TEAEs.

AEs are considered serious and require expedited reporting if they meet the definition of a **Serious Adverse Event** (see part below).

11.3.2.2 Serious Adverse Event (SAE)

An SAE is an AE (untoward medical occurrence) that fulfills at least one of the following criteria:

- results in death;
- is life-threatening (immediate risk of death);
- requires inpatient hospitalization or prolongation of existing hospitalization;
- results in a persistent or significant incapacity or substantial disruption of the ability to conduct normal life functions;
- is a suspected transmission of any infectious agent via a medicinal product (medically significant) and should be reported as an SAE in the category "*Other medically important conditions*";
- results in a congenital anomaly/birth defect;
- is another medically significant event (i.e. a medically significant condition that may jeopardize the subject or require medical or surgical intervention to prevent any of the previously listed outcomes). Medical and scientific judgment should be exercised in deciding whether expedited reporting is appropriate in situations other than those listed above. Examples of such medical events include allergic bronchospasm requiring intensive treatment in an Emergency Room or at home, blood dyscrasia, or convulsions that do not result in hospitalization; or development of drug dependency or drug abuse, or malignancy).

